7. STUDY TREATMENT

7.1. Study Treatment Administered

Ruxolitinib 5 mg tablets or matching placebo will be administered BID approximately 12 hours apart (morning and night) without regard to food/feeding. One or 3 tablets will be administered per dose, depending on the assigned treatment arm (ie, 1 tablet per dose for 5 mg ruxolitinib/placebo and 3 tablets per dose for 15 mg ruxolitinib/placebo).

Initially, ruxolitinib will be administered through an enteric feeding tube as follows:

- Suspend tablet(s) in approximately 40 mL of water with stirring for approximately 10 minutes.
 - For 5mg BID ruxolitinib/placebo treatment assignment: one 5 mg tablet in 40 mL water
 - For 15 mg BID ruxolitinib/placebo treatment assignment: three 5 mg tablets in 40 mL water

Within 6 hours after the tablet has dispersed, the suspension can be administered through the enteric feeding tube using an appropriate syringe.

• The tube should be rinsed with approximately 75 mL of water.

Dosing of ruxolitinib during prone positioning is permitted if consistent with institutional policy. If enteric medication administration is not possible during prone positioning, administration of ruxolitinib should occur before or after proning sessions, adhering as closely to the BID dosing schedule as possible.

If a participant is extubated during the study and is able to take oral medication, study drug may be administered orally with water, without regard to food.

The recommended duration of treatment is up to 14 days. Beginning on Day 15, treatment may be extended another 14 days (through Day 28) at the discretion of the investigator, if the benefits of treatment outweigh the risks, and with approval from the sponsor medical monitor.

Dose reductions or interruptions for any toxicity attributed to ruxolitinib are permitted to allow the participant to continue on study treatment (see Section 7.6.2).

Table 5 presents the study treatment information.

Table 5:Study Treatment Information

Investigational/Control Drug	Pharmaceutical Dosage Form	Route of Administration	Supply Type
Ruxolitinib 5 mg	Tablet	Enteric feeding tube or oral	Double-blind supply; bottles
Placebo for 5 mg ruxolitinib	Tablet	Enteric feeding tube or oral	Double-blind supply; bottles

7.1.1. Supply of Study Treatment

No additional treatment beyond ruxolitinib 5 mg tablets or matching image placebo tablets will be provided. Ruxolitinib will packaged in 60-count high-density polyethylene bottles. All tablet excipients comply with the requirements of the applicable compendial monographs.

If the participant continues treatment beyond the initial 14-day treatment period, if needed, the IRT should be contacted to dispense additional study drug.

7.1.2. Treatment Duration

The planned initial duration of treatment is 14 days. Treatment may be extended to an additional 14 days (ie, Days 15-28) at the discretion of the investigator, if the benefits of treatment outweigh the risks, and with approval from the sponsor medical monitor. Approval must be requested \geq 24 hours before initiation of dosing on Day 15. Participants may be discontinued from treatment earlier due to unacceptable toxicity, progression/worsening of COVID-19 ARDS, or resolution/improvement of COVID-19 symptoms and/or at the discretion of the investigator or the participant. Treatment will not be provided upon completion of the study.

7.2. Other Treatments

7.2.1. Concomitant Therapy

All medications, procedures, and significant nondrug therapies administered from randomization through Day 29 must be recorded on the appropriate eCRFs. Additionally, antivirals and therapeutic agents administered for SaRS-CoV-2 infection/COVID-19 infection and treatments for COVID-19–associated ARDS administered within 14 days of randomization must also be recorded.

Each concomitant drug must be individually assessed against all exclusion criteria/prohibited medication. If in doubt, the investigator should contact the Incyte medical monitor before randomizing a participant or allowing a new medication to be started. If the participant is already enrolled, contact Incyte to determine if the participant should continue participation in the study.

7.2.1.1. Permitted Concomitant Therapy Requiring Caution and/or Action

Participants may receive the following (not inclusive): antiemetics, calcineurin inhibitors, azole fungal prophylaxis, antibiotics, acyclovir prophylaxis, granulocyte-colony stimulating factor, corticosteroid premedications prior to RBC/platelet transfusions, narcotics, and sedatives; however, close monitoring of potential drug-drug interaction effects of these concurrent drugs is warranted.

Use of oral, injected, or implanted hormonal methods of contraception are allowed while on ruxolitinib.

In the presence of potent CYP3A4 inhibitors, there is the possibility of increased exposure to ruxolitinib. Dose adjustment when coadministering ruxolitinib and a potent CYP3A4 inhibitor is only required for participants assigned to the 15 mg BID ruxolitinib/placebo arm; see Section 7.2.1.2 for additional details. No dose adjustment is required for participants

randomized to the 5 mg BID ruxolitinib/placebo arm. See Appendix D for a list of CYP3A4 inhibitors and inducers.

The participant and the treating investigator should be aware of potential signs of overdose of the concomitant medications; in the event of suspected study drug–related toxicity, administration of ruxolitinib should be dose reduced or held according to the treating investigator's judgement.

For additional information, please refer to the IB.

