5.5. Purpose and Timing of Interim Analyses/Design Adaptations

A DMC will be formed. The DMC will consist of qualified individuals who are not involved with the conduct of the study. The establishment, composition, roles, duties, and responsibilities of the DMC are addressed in the approved DMC charter. Additional details regarding interim analyses may be found in Section 12.5.

There will be 1 planned interim analysis conducted for efficacy based on the first 40% of participants enrolled in the study. The efficacy interim analysis will be conducted when the first 40% of the planned randomized participants (approximately 200 randomized participants) have died or have reached their Day 29 assessment. Based on the results of this interim analysis, the DMC may choose to terminate the study for positive efficacy or continue the study with no changes to enrollment.

5.6. **Risks and Benefits**

There is preclinical evidence from both laboratory and animal models that blockade/inhibition of the JAK-STAT pathway could have a beneficial effect on cytokine storm and the course of ARDS in patients with COVID-19. Additionally, there is clinical evidence of efficacy with ruxolitinib in pilot studies in another recognized disease associated with CRS/cytokine storm: sHLH (see Section 5.3). However, ruxolitinib has not previously been studied in patients with COVID-19–associated ARDS. Therefore, it is unknown as to whether there will be a benefit for patients being treated with ruxolitinib in this disease.

The primary clinical risks with ruxolitinib treatment are the potential sequelae of decreased hematopoietic proliferation attributable to the inhibition of growth factor pathways associated with JAK inhibition. In the Phase 3 clinical studies of ruxolitinib in participants with MF, which involved longer-term dosing and, in general, higher doses than those proposed in this Protocol, the most frequent TEAEs were dose-dependent, reversible thrombocytopenia, anemia, and neutropenia. These events could increase the risk of infection, including pneumonia and

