7.6.2. Recommended Treatment of Adverse Events

Dose reductions or interruptions for worsening cytopenias attributed to ruxolitinib/placebo are permitted to allow the participant to continue on study treatment. Table 6 describes dose levels of ruxolitinib by treatment arm. Dose adjustments for different ranges of cytopenias are described in the following text. Use of transfusion support is allowed during the study.

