7.6.2.2. Thrombocytopenia

Transfusion support should be provided as clinically indicated.

For platelet counts $< 20 \times 10^9$ /L: hold dose until resolved to $\ge 20 \times 10^9$ /L and then resume at 1 dose level lower. If counts are stable, dose may be cautiously re-escalated to initial dose level.

Dose reductions or interruptions for nonhematologic toxicity are permitted to allow the participant to continue on study treatment. Dose adjustments for different ranges of nonhematologic toxicity are described in the following text. The objective of the dose

adjustment rules is to optimize treatment response for each individual participant while avoiding significant nonhematologic toxicities.

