#### 9.3.2. Laboratory Value Summaries

Any laboratory test results and associated normal ranges from local laboratories will be converted to SI units. Scheduled laboratory tests for hematology and clinical chemistry will be summarized by scheduled study days (eg, Days 3, 5, 7) through Day 29. Windows for postbaseline by-visit summaries will be  $\pm 1$  study day (eg, Day 3 will be Days 2-4).

When there are multiple nonmissing laboratory values for a participant's particular test within a visit window, the convention described in Table 5 will be used to determine the record used for by-visit tabulations and summaries. A record may only be used for 1 scheduled visit. If a record qualifies for more than 1 by-visit summary, then the earlier study day will take precedence.

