**Table 5: Identification of Records for Postbaseline By-Visit Summaries**

Priority	Laboratory Visit	Proximity to Visit Window	Tiebreaker
1	Scheduled	In-window	Use smallest laboratory sequence number
2	Unscheduled	In-window	
3	Scheduled	Out-of-window	

Numeric laboratory values will be summarized descriptively in SI units, and non-numeric test values will be tabulated when necessary. In addition, line graphs and box-and-whisker plots will

be provided for hemoglobin, platelet counts, leukocytes, lymphocytes, neutrophils, creatinine, ALT, and AST.

Severity grades will be assigned to laboratory test values based on the numerical component of CTCAE v5. Shift tables will be presented showing change in CTCAE grade from baseline to worst grade postbaseline. Separate summaries for abnormally high and abnormally low laboratory values will be provided when the laboratory parameter has both high and low grading criteria. The denominator for the percentage calculation will be the number of participants in the baseline category. Shift tables will also be presented showing change in CTCAE grade from baseline to the last value using the same methods explained above. The number of participants who experienced worsening of laboratory abnormalities will be summarized by maximum severity.

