## Listings

Listing No.	Title
2.1.1	Participant Disposition Status
2.1.2	Participant Enrollment and Site Information
2.2.1	Protocol Deviations
2.2.2	Randomized Participants With Inclusion/Exclusion Criteria Violations
2.3	Analysis Population
2.4.1	Demographic and Baseline Characteristics
2.4.2	Medical History
2.4.3	COVID-19 Baseline Disease Characteristics
2.4.4	Prior Medications for COVID-19
2.4.5	Prior and Concomitant Medications
2.4.6	PBRC/Platelet Transfusions
2.4.7	Procedures and Non-Drug Therapies
2.5.1	Ruxolitinib/Placebo Exposure and Compliance
2.6.1	Deaths and 28-Day Mortality
2.6.2	COVID-19 Ordinal Scale by Study Day
2.6.4	COVID-19 Improvement Events and Assessment
2.6.5	Hospitalization, Ventilation, and Intubation Status
2.6.6	SOFA Scores and Components by Study Day

Listing No.	Title
2.6.7	Arterial Blood Gas Analyses
2.6.8	Deaths
2.6.9	Chest Imaging
2.6.10	Concomitant IL-6, IL-6R, IL-1RA, IL-1 beta, GM-CSF, BTK, or JAK Directed Therapies
2.6.11	Serum Markers of Inflammation
2.6.12	SARS-CoV2 Virology
2.6.13	SARS-CoV2 Serology
2.7.1	Adverse Events
2.7.2	Serious Adverse Events
2.7.3	Grade 3 and Higher Adverse Events
2.7.4	Fatal Adverse Events
2.7.5	Ruxolitinib/Placebo Treatment-Related Adverse Events
2.7.6	Serious Ruxolitinib/Placebo Treatment-Related Adverse Events
2.7.7	Adverse Events Leading to Ruxolitinib/Placebo Dose Interruption
2.7.8	Adverse Events Leading to Ruxolitinib/Placebo Dose Reduction
2.7.9	Adverse Events Leading to Discontinuation of Ruxolitinib/Placebo
2.8.1.1	Abnormal Clinical Laboratory Values - Hematology
2.8.1.2	Clinical Laboratory Values - Hematology
2.8.1.3	Abnormal Clinical Laboratory Values - Chemistry
2.8.1.4	Clinical Laboratory Values - Chemistry
2.8.1.5	Potential Drug Induced Liver Injuries
2.8.2.1	Abnormal Vital Sign Values
2.8.2.2	Vital Sign Values

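### By-visit and last-value blood counts ignore earlier transfusion or G-CSF, and no table counts transfusions by arm, so these two displays can attenuate a cytopenia difference from placebo

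*Protocol*

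**What the plan says.** **Risk.** Protocol 5.6 states: "The primary clinical risks with ruxolitinib treatment are the potential sequelae of decreased hematopoietic proliferation". In the Phase 3 myelofibrosis studies, "the most frequent TEAEs were dose-dependent, reversible thrombocytopenia, anemia, and neutropenia".

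**Rescue.** Among the permitted therapies, Protocol 7.2.1.1 lists "granulocyte-colony stimulating factor, corticosteroid premedications prior to RBC/platelet transfusions". The transfusion words there concern premedication. The permission itself is in Protocol 7.6.2, in the cytopenia dose-adjustment text: "Use of transfusion support is allowed during the study". Section 7.6.2.2, on thrombocytopenia, adds: "Transfusion support should be provided as clinically indicated".

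**Laboratory displays.** SAP 9.3.2 states: "Scheduled laboratory tests for hematology and clinical chemistry will be summarized by scheduled study days (eg, Days 3, 5, 7) through Day 29". SAP Table 5 chooses among records by scheduled or unscheduled status, visit window and sequence number. The same section adds: "Shift tables will also be presented showing change in CTCAE grade from baseline to the last value using the same methods explained above". SAP 4.1.4 takes the last available value to be the last nonmissing one after the start of treatment, up to 31 days after the last dose. None of these rules mentions transfusion or G-CSF.

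**Rescue in the outputs.** Transfusions have Listing 2.4.6, titled "PBRC/Platelet Transfusions", and no table in SAP Appendix A is devoted to them. G-CSF is counted by arm only as one entry in the general concomitant-medication table (1.4.2; SAP 6.6) and is not linked to neutrophil counts.

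**The concern.** Rescue is given because a count is low, and it raises the count that is then summarised. If ruxolitinib lowers counts, its arms should need rescue more often, and their later counts move back toward placebo. The by-visit means and the last-value grades then describe drug plus rescue against placebo plus less rescue. Part of the difference moves into the rescue rates, and for transfusion no planned table shows those rates by arm.

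The safety objective compares each dose with placebo and includes clinically significant laboratory changes. A reader of the by-visit or last-value hematology tables alone could conclude that the arms are more alike than the drug made them.

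**Working it through.** The documents state no rate of cytopenia, transfusion or G-CSF use, so there is no figure of the plan to reproduce. The check is of the text, followed by illustrations on assumed inputs.

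**1. Which displays are exposed**

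| Planned display | Keeps a low count measured before rescue? |
|---|---|
| By-visit values, changes and plots (3.3.1.1, Figure 4.6.1) | At that visit only; later visits use the raised count |
| Shift to last value (3.3.5.1) | No, if the last count is a raised one |
| Shift to worst grade (3.3.3.1) | Yes |
| Treatment-emergent worsening (3.3.3.3) | Yes |
| Adverse-event tables (3.2.x) | Yes, if reported as an event |

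Only the first two rows are at issue.

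**2. Last-value grade, by arithmetic.** If rescue lifts a fraction r of severe cases above the grade limit, equally in both arms, the shown difference is the true difference × (1 − r).

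- Assumed true Grade 3 or higher rates of 15% and 5%: 10 points × (1 − 0.25), × (1 − 0.50) and × (1 − 0.75) give 7.5, 5.0 and 2.5 points.
- Assumed rates of 25% and 10%: 15 points become 11.25, 7.5 and 3.75.

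**3. By-visit hemoglobin mean, by simulation.** Daily value = baseline − (common fall + drug fall) × (day − 1) + noise + 1 g/dL for each earlier transfusion. A transfusion follows any value below the trigger. Baseline SD is 1.6, noise SD is 0.35, and there are 200,000 simulated participants per arm. All inputs are assumptions, and no trigger is a recommendation. Share lost = 1 − shown difference / untreated difference, from unrounded means.

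| Baseline (g/dL); common fall; drug fall (g/dL per day) | Untreated Day 15 difference | Shown at trigger 7 / 8 / 9 | Share lost |
|---|---|---|---|
| 10.5; 0.10; 0.07 | −0.97 | −0.76 / −0.57 / −0.38 | 22% / 42% / 61% |
| 11.5; 0.05; 0.07 | −0.97 | −0.93 / −0.85 / −0.70 | 4% / 13% / 28% |
| 12.5; 0.05; 0.035 | −0.48 | −0.48 / −0.47 / −0.44 | 1% / 3% / 10% |

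The untreated values agree with 14 × 0.07 = 0.98 and 14 × 0.035 = 0.49 up to simulation error. In the first row, the proportions transfused through Day 15 (drug vs placebo) are 28% vs 13%, 51% vs 30% and 74% vs 54%: the signal has moved into the rescue rates. The share with worst hemoglobin below 8 g/dL stays at about 51% vs 30% for triggers up to 8. It falls to about 7% in both arms at a trigger of 9, because transfusion then comes before that level is reached.

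**4. Platelets, by simulation.** Assumed median baseline is 220 × 10^9/L, with counts below 50 removed as in exclusion criterion 16, and a mean fall by Day 15 of 35% on drug and 5% on placebo. With transfusion below 50 and a lift of 20 to 40, the last-value difference in the share below 50 falls from 8.3 points to 7.0 or 5.5. The Day 15 mean difference barely moves (about −73.6 to −73.0 or −72.3), and the worst-value difference stays at 8.4 points. With transfusion only below 20, almost nothing changes. Neutrophils and G-CSF were not modelled.

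**The case against.** **Cytopenia is reported elsewhere.** Protocol 11.1 makes an abnormal laboratory result an adverse event when it needs treatment or a change in study drug, preferably recorded as a diagnosis such as anemia. Such events are tabulated by arm: overall, at Grade 3 or higher, leading to dose reduction or interruption, and requiring concomitant medication (Table 3.2.21). The worst-grade and worsening tables stand beside them. This objection stands and sets the limit of the point. A reader might infer that the plan as a whole conceals the expected toxicity; these tables do not support that. What remains is that Table 3.2.21 does not isolate transfusion or G-CSF, and that no worst-value table can record a nadir that early transfusion prevented.

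**As-measured summaries are legitimate.** Protocol 12.4.2 plans no formal comparison of laboratory data, and counts under actual care are a proper description. This stands: the as-measured tables should stay. It does not explain why transfusion is not counted by arm.

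**The size depends on the inputs.** This stands. Taking 22% to 61% as the expected loss would select the least favourable inputs; the milder rows give 1% to 28%. Protocol 5.6 also reports weaker blood-cell effects in several groups without myelofibrosis, and initial treatment lasts 14 days.

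**The loss is dose-related.** A reader might infer this from the dose-dependence in Protocol 5.6. The calculations compare one drug arm with placebo, and the documents give no rescue rates by dose, so it is not shown.

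**Rescue has other causes.** Ventilated patients may be transfused for reasons unrelated to the drug, including bleeding where anticoagulation is allowed. This stands as a reason to read any rescue count descriptively.

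**Conclusion.** The gap holds in a limited form. SAP 9.3.2 and 4.1.4 give no rule for counts taken after transfusion or G-CSF, and no planned table counts transfusions by arm. If ruxolitinib lowers counts and rescue follows low counts, the by-visit and last-value hematology displays can attenuate the difference from placebo. The size cannot be derived from the documents. Under the assumed hemoglobin inputs it runs from about 1% to 61% of the Day 15 mean difference. For platelets, the last-value grade is affected more than the mean, and neither is affected much if transfusion is rare. The conclusion does not extend to the worst-grade, worsening or adverse-event tables for any nadir measured before rescue. No test or decision rule depends on the exposed displays. This is a worthwhile low-cost addition to safety reporting and casts no doubt on the primary analysis.

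**What to change.** **Add one by-arm safety table to SAP Appendix A.** Give the number (%) of participants with at least one red-cell transfusion, platelet transfusion or G-CSF dose through Day 29, each shown separately. For each cell line, add the composite of worst CTCAE Grade 3 or higher or the corresponding rescue: hemoglobin with red-cell transfusion, platelets with platelet transfusion, neutrophils with G-CSF.

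**Mark post-rescue counts in SAP 9.3.2.** Either flag them in the by-visit and last-value hematology summaries, or repeat those summaries without them, as a supplement to the as-measured ones. Do not carry the pre-rescue count forward: Protocol 5.6 calls these cytopenias reversible, and a frozen value would erase real recovery after dose reduction or interruption. Leaving post-rescue counts out removes selected participants, which is why it should only supplement the full table.

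**Cost.** One or two extra tables and a few sentences in SAP 9.3.2. Protocol 7.2.1 already has medications and procedures recorded from randomization through Day 29, and transfusions are already listed. A last value after Day 29 falls outside that recording period and should be marked as unclassified.

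**Limits.** Some rescue has non-drug causes, so the composite should be descriptive and shown beside its components. With 211 randomized 2:2:1, placebo has about 211 / 5 = 42 participants, so the counts will be small. No clinical rule changes.

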7.2.1.2. Coadministration With Potent CYP3A4 Inhibitors

Coadministration of ruxolitinib and potent CYP3A4 inhibitors may result in increased ruxolitinib exposure; in the setting of potent CYP3A4 inhibitors (see Appendix D for a list), participants assigned **to the 15 mg BID ruxolitinib/placebo arm only** should be reduced 1 dose level (see Table 6) with daily complete blood cell count monitoring during the period of coadministration.

7.2.1.3. CRRT and Intermittent Hemodialysis

If a participant requires CRRT during the study treatment period, the ruxolitinib/placebo dose frequency should be reduced from BID to QD. If a participant requires intermittent hemodialysis during the study treatment period, the assigned ruxolitinib/placebo dose should only be given on hemodialysis days and following each hemodialysis session.

7.2.2. Prohibited Medication

The following medications are prohibited until treatment discontinuation:

- Concomitant use of another JAK inhibitor or IL-6/IL-6R, IL-1RA, IL-1 β , or GM-CSF antibodies.
- Any investigational medication except antivirals being used to treat SARS-CoV-2 infection or ARDS.
- Aspirin in doses exceeding 150 mg/day.

For additional information, refer to the IB.

7.3. Participant Numbering, Treatment Assignment, and Randomization

7.3.1. Participant Numbering

Each participant is identified in the study by a participant number that is assigned by the IRT when the participant is enrolled for screening and is retained for the participant throughout participation in the study. A new participant number will be assigned at every subsequent enrollment if the participant is rescreened. The participant number consists of the center number (as assigned by Incyte to the investigative site) with a sequential participant number suffixed to it so that each participant's participation is numbered uniquely across the entire database. Upon signing the ICF (or having the consent signed on their behalf by their legal guardian/health care proxy) and assent (if applicable), participants are assigned to the next sequential participant number available.

